#### F. Allocation of interventions

- **a. Methods for randomisation and stratification.** PCCs in clinics randomized to Opioid Wizard (in 15 of the 30 clinics randomized in the parent study) will be randomized 1:1 to the stigma reduction or comparison training, stratified by clinic and waiver status. Randomization will be generated using SAS software.
- b. Methods for concealment of allocation. PCCs will be blind to their randomized MyLearning training assignment. The study statistician ([name]) will generate the randomization assignment, and a study team member will submit that list to HP MyLearning staff. Study team members capturing outcome data from surveys, Opioid Wizard, and Epic (including use rates, buprenorphine prescriptions) will also be blind to treatment assignment.

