# c. Secondary Outcome Measures

- i. Waivered PCC prescribing and referral behavior. As an exploratory outcome, we will gather the rate of MOUD, naloxone, and opioid prescriptions and referrals to waivered clinicians (primary care and specialty addiction medicine) among eligible patients in the 12 months prior to the study and during the 6-month follow-up period to determine whether the stigma reduction and/or control training affected change in prescribing behavior.
- ii. PCC waiver status. In addition to intentions to get waivered, change in waiver status will be collected as an exploratory outcome. A list of waivered PCCs will be pulled from HP administrative data to determine if additional PCCs became waivered during the follow-up period.
- iii. *PCC willingness to work with people with OUD.* PCCs will report on their willingness to work with people with OUD using 3 items adapted from the Drug Problems Perceptions Questionnaire.  PCCs will respond to each item using a 5-point Likert-type scale ranging from 1 (*strongly disagree*) to 5 (*strongly agree*). One item is reverse scored ("I would enjoy my job more if I could stop working with patients with opioid use disorder") and the items will be averaged for a total score, with higher scores corresponding to greater willingness to work with people with OUD.
- iv. PCC opioid treatment outcome expectancies. Treatment outcome expectancies will be assessed using two items developed for this study. First, PCCs will rate the extent to which they believe available treatments are effective for treating OUD on a 4-point Likert-type scale ranging from 1 (not at all effective) to 4 (very effective). The second item will ask PCCs to rate the extent they believe patients will comply with those treatments on a 4-point Likert-type scale ranging from 1 (not at all likely) to 4 (very likely). Items will be analysed separately.
- v. PCC perceptions of the training and the Opioid Wizard tool. In the initial survey, PCCs will provide feedback on the training in four questions, including their perception of the usefulness and ease of use of the training and their intentions to use the Opioid Wizard tool. At the 3-month follow-up survey, these questions will be replaced with items specifically about Opioid Wizard, not the training, to assess likelihood of recommending Opioid Wizard to colleagues, frequency of using Opioid Wizard, Opioid Wizard ease of use, and intention to use Opioid Wizard in the future.

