#### d. Covariates

i. Demographics. PCCs will report on their demographic characteristics, including gender, age, race, ethnicity, and days per week in clinic in the survey. HealthPartners administrative data will be used to determine clinician type (MD/DO, nurse practitioner, or physician assistant).

- **ii.** *Frequency in addressing OUD.* PCCs will report on the frequency with which they typically address OUD in their practice using one item: How often do you treat patients with opioid use disorder? Response options will be on a 5-point Likert-type scale ranging from 1 (*never*) to 5 (*daily*).
- iii. PCC perceived vulnerability to OUD. PCC perceived vulnerability to developing OUD will be assessed using 3 items. PCCs will rate the extent they agree with each statement on a 5-point Likert-type scale ranging from 1 (strongly disagree) to 5 (strongly agree). One item will be reverse-scored ("If I were prescribed opioids, there is a real risk I would become addicted"). Items will be averaged for a total score, with higher scores corresponding to lower perceived vulnerability to OUD.

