# L. Sample size

There are 449 PCCs in the 30 clinics being considered for randomization to the parent study, COMPUTE 2.0, with an average of 15 per clinic (range 4-36). To the extent that the parent study will seek balance between treatment arms in clinic size, and by extension number of PCCs, we estimate that 225 PCCs will be in intervention clinics and eligible for this study. We have estimated power for PCC participation rates of 50%, 65%, and 80% with equal numbers of PCCs per arm. Approximately 93% of PCCs at HP are not waivered, which would reduce available sample sizes for H1b and H1c to 208 PCCs. The power analysis was calculated using G\*Power 3.1 and determined the minimal detectable standardized effect between groups for each outcome given available sample size,  $\alpha_2$  = .05, and desired power (see Table 1). Given these assumptions, we will have the ability to detect moderate differences (80% power: d = 0.42-0.55; RR=1.28-1.58) between the groups.

For Aim 2, the regression models will include PCCs in both arms and up to 4 covariates. Given sample size,  $\alpha_2$  = .05, and desired power, we will have adequate power to detect small effects for H2a (80% power:  $f^2$  = 0.05-0.08) and moderate effects for H2b (80% power: RR=1.29-1.60).

Table 1. Minimal detectable	Table 1. Minimal detectable standardized effects based on PCC						
participation rate and desired power.							
PCC participation= 50% 65% 80%							

	112 F	PCCs	146 F	PCCs	180 F	PCCs	
ро	wer =	0.80	0.90	0.80	0.90	0.80	0.90
H1a: OUD Stigma	d	0.49	0.57	0.47	0.54	0.42	0.49
H1b, H1c: Intentions	d	0.55	0.64	0.48	0.56	0.44	0.51
H1d: CDS Use: 30%	RR	1.58	1.69	1.50	1.59	1.44	1.52
50%	RR	1.44	1.51	1.38	1.44	1.34	1.39
70%	RR	1.36	1.43	1.31	1.37	1.28	1.33
H2a: Intentions	f 	0.08	0.10	0.06	0.08	0.05	0.06
H2b: CDS Use: 30%	RR	1.60	1.71	1.52	1.61	1.46	1.54
50%	RR	1.45	1.53	1.39	1.46	1.35	1.41
70%	RR	1.37	1.44	1.32	1.38	1.29	1.34
Note. Cohen's d = d; Co	hen's	$f^2 = f^2; I$	Rate ra	tio = RF	₹.		

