# M. Analysis Strategies

All variables will be examined using descriptive statistics and graphical methods to examine distributions, potential outliers, and analysis assumptions across and within study arms. The hypotheses predict that PCCs in the stigma reduction intervention will report less stigma of people with OUD and greater intentions to get waivered and prescribe buprenorphine (among non-waivered PCCs), and will use Opioid Wizard at a greater proportion of eligible encounters. A generalized linear model framework will be used to test the Aim 1 hypotheses, using appropriate error distributions and link functions to normalize outcomes. For H1a through H1c, the primary outcomes will be stigma (H1a) and intentions to get waivered (H1b) and to prescribe buprenorphine (H1c), assessed immediately following the training; as a secondary outcome, we will examine whether the intervention has enduring effects on stigma and intentions by examining differences assessed at the 3-month follow-up survey. Secondary analyses will include an interaction term between intervention arm and waiver status to assess treatment heterogeneity.

In Aim 2, multiple linear regression models, controlling for PCC characteristics (i.e., age, gender, PCC type [physician, nurse practitioner, physician assistant], and waiver status [H2b only]) will be used to examine whether self-reported OUD stigma is related to (1) intention to get waivered to prescribe buprenorphine and (2) Opioid Wizard use. Secondary analyses will include an interaction term between stigma and waiver status to examine whether waiver status moderates the association between stigma and Opioid Wizard use.

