In secondary analysis, we will examine whether self-reported stigma mediates the effect of the intervention on Opioid Wizard use. If the intervention affects Opioid Wizard use (H1d), and stigma is related to Opioid Wizard use (H2b), we will use a product of coefficients approach to quantify how much of the intervention effect is mediated by stigma. In other exploratory analyses, we will examine whether PCCs in the stigma reduction arm prescribe MOUD and /or naloxone to eligible patients at a higher rate than PCCs in the comparison arm, controlling for pre-Opioid Wizard prescribing behavior. We will also examine whether PCCs in the stigma reduction arm prescribe opioids to eligible patients at a lower rate than PCCs in the comparison arm, controlling for pre-Opioid Wizard prescribing behavior. Further, as a follow-up to H1b, we will examine whether PCCs in the stigma reduction arm are more likely to get waivered than control PCCs using a logistic regression framework. To understand how PCC experience with patients at high risk for problems with opioids may have influenced their decision to participate in this study, we will compare PCC prescribing and referral behaviors among PCCs who completed the training to those who did not among all randomized PCCs.

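### Aim 1 prespecifies no baseline covariates, although clinician type and 12-month prescribing and referral history are collected; adjusting for them costs little, for a gain of unknown size that is best supported for H1d

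*Combined protocol and SAP*

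**What the plan says.** - Section M, on H1a–H1d: "A generalized linear model framework will be used to test the Aim 1 hypotheses, using appropriate error distributions and link functions to normalize outcomes". No covariate is named, nor either stratification factor. Waiver status appears only in a secondary interaction with arm.
- Section F.a: PCCs "will be randomized 1:1 to the stigma reduction or comparison training, stratified by clinic and waiver status".
- Section M does name covariates for other analyses. Aim 2 adjusts for age, gender, clinician type and (H2b only) waiver status. The exploratory prescribing comparisons are made "controlling for pre-Opioid Wizard prescribing behavior".
- Section H.d (Covariates): "HealthPartners administrative data will be used to determine clinician type". It does not say which models use the variables listed there.
- Section H.c.i: prescribing and referral rates are gathered "among eligible patients in the 12 months prior to the study and during the 6-month follow-up period". That item's heading refers to waivered PCCs, whereas Section E.a and the end of Section M speak of prescribing and referral data for all randomized clinicians.
- Section L mentions covariates only in the Aim 2 power statement.

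**The concern.** There is no baseline survey: self-reported outcomes are first measured right after training (Sections D.c and H.a). The planned information that predates training is therefore clinic, waiver status, clinician type, and prescribing and referral history. As written, the exploratory prescribing outcomes get baseline adjustment and the primary hypotheses do not.

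Two things are at stake. The first is precision: Section L gives detectable differences of d = 0.42–0.55 at 80% power for H1a–H1c, so a modest improvement would be useful. The second is an open choice of covariates. The Section H.d list includes frequency of treating OUD and perceived vulnerability to OUD, both answered in the post-training survey (Appendix D, items 6 and 16–18). Patient narratives could plausibly shift perceived vulnerability. An analyst who took that list as the Aim 1 covariate set could adjust for something the intervention had changed and so distort the arm effect.

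**Working it through.** **Inputs.** Section L: "we estimate that 225 PCCs will be in intervention clinics and eligible for this study"; participation of 50%, 65% or 80%, split evenly between the arms; two-sided α = 0.05. Table 1 uses N = 112, 146 and 180. For H1b/H1c, 93% are non-waivered: 0.93 × 112 = 104.2, 0.93 × 146 = 135.8 and 0.93 × 180 = 167.4, taken as 104, 136 and 168 to give equal arms.

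**Step 1: reproduce Table 1 without covariates.** For H1a–H1c the test is a two-sample t-test with noncentrality d√N/2 and N − 2 df. Detectable d at 80% power:

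| Hypothesis | N | Computed | Table 1 |
|---|---|---|---|
| H1a | 146 | 0.467 | 0.47 |
| H1a | 180 | 0.420 | 0.42 |
| H1b/H1c | 104 | 0.555 | 0.55 |
| H1b/H1c | 136 | 0.484 | 0.48 |
| H1b/H1c | 168 | 0.435 | 0.44 |

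The H1a column for 112 PCCs does not reproduce (computed 0.53 at 80% and 0.62 at 90% power, stated 0.49 and 0.57). That is a separate matter and does not bear on this point.

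For H1d, a Wald Poisson formula with a standard-normal predictor fits: N = (1.960 + 0.842)² × exp(−b²/2) / [p × b² × (1 − R²x)], with b = ln RR and base rate p. With R²x = 0, p = 0.3 and RR = 1.582, b² = 0.210 and N = 7.85 × 0.900 / (0.3 × 0.210) ≈ 112. Across N = 112, 146 and 180:

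| Base rate | Computed RR | Table 1 |
|---|---|---|
| 30% | 1.582, 1.501, 1.446 | 1.58, 1.50, 1.44 |
| 50% | 1.437, 1.377, 1.335 | 1.44, 1.38, 1.34 |
| 70% | 1.362, 1.313, 1.279 | 1.36, 1.31, 1.28 |

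All agree within 0.01. The H2b cells reproduce with R²x = 0.05 (at 30%: 1.599, 1.516, 1.459 against 1.60, 1.52, 1.46). A covariate allowance was therefore made for H2b and none for Aim 1. R²x is the share of the predictor explained by covariates, so it raises N. It is not the outcome R² used next.

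**Step 2: gain for H1a–H1c.** If baseline covariates explain a share R² of outcome variance, residual variance is multiplied by 1 − R² and the noncentrality is divided by √(1 − R²). Starting from 80% power, power ≈ Φ(2.802/√(1 − R²) − 1.960). At R² = 0.10 this is Φ(2.802/0.9487 − 1.960) = Φ(0.993) = 0.84. Detectable d is multiplied by √(1 − R²). R² is an assumption throughout.

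| R² | Power | d, H1a, N = 180 | d, H1b/H1c, N = 104 | Total N for d = 0.42 (normal approx.) |
|---|---|---|---|---|
| 0 | 80% | 0.420 | 0.555 | 178 |
| 0.01 | 80.4% | 0.418 | 0.552 | 178 |
| 0.05 | 82% | 0.409 | 0.541 | 170 |
| 0.10 | 84% | 0.398 | 0.526 | 162 |
| 0.20 | 88% | 0.376 | 0.496 | 144 |

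**Step 3: cost if the covariates predict nothing.** At N = 104 and d = 0.55, power is 79.3% unadjusted. With six covariate df spent and R² = 0 it is still 79.3%. Terms for the stratification factors are not counted in the six.

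**Step 4: H1d.** No gain is computed. The number of eligible visits per PCC is not given, and the Table 1 rate ratios match a standard-normal predictor, not a two-arm contrast. The argument comes from the text: Section H.b.iv counts giving a referral, prescribing a medication and prescribing naloxone as Opioid Wizard use. These are the kinds of behaviour the 12-month history records, and Section E.a puts all randomized clinicians in this analysis.

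**The case against.** **Silence is not a decision.** A reader might infer that Aim 1 will ignore these variables. The documents do not say so: a generalized linear model can hold covariates, Section H.d lists clinician type without limiting it to Aim 2, and nothing states that Aim 1 is unadjusted. This stands, and the point is limited to what is prespecified.

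**The gain may be trivial.** A reader might also infer that the trial gives up power on all four primary hypotheses. That is not shown, because the documents give no correlation between these variables and any primary outcome. H1b/H1c include only non-waivered PCCs, so buprenorphine history should hardly vary there, and about 93% of the H1a sample is also non-waivered. History may be noisy as well: at the Section D.b minimum of 50 eligible patients per clinic and the Section L average of 15 PCCs, there are 50/15 ≈ 3.3 patients per PCC. Actual counts may be higher. This stands as to size for H1a–H1c.

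**Waiver status is already balanced by design.** Waiver status and clinic are stratification factors and are known before training, so the R² that matters is the increment over them. This stands.

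**Adjustment has conditions.** A rate among eligible patients is undefined for a PCC with none. With a logit link, adjustment changes the odds ratio being estimated. The history may be pulled only for waivered PCCs, as the Section H.c.i heading suggests. These stand and are handled in the fix.

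None of this removes the point. The same section names covariates for lesser analyses, and naming them for Aim 1 loses almost nothing if they prove uninformative.

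**Conclusion.** The point holds as a gap in prespecification with a likely but unquantified efficiency benefit. Aim 1 names no baseline covariate, and its power figures allow for none. For the continuous outcomes the gain is about 2 points of power at R² = 0.05, 4 at 0.10 and 8 at 0.20, and nil at R² = 0. Those R² values are assumed. The case is strongest for H1d, on the definition of use, and less certain for the attitude and intention outcomes.

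This does not make the planned comparison invalid: an unadjusted randomized comparison is sound. The conclusion assumes that the history exists for all randomized PCCs and that the covariates are fixed before training.

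**What to change.** Add to Section M:

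- **H1d:** adjust the arm effect for clinician type, the PCC's 12-month pre-study MOUD/naloxone prescribing and referral rate among eligible patients, and the stratification factors. Use a missing-indicator category for PCCs with no eligible patients or no history.
- **H1a–H1c:** adjust for clinician type and, expecting a smaller and less certain gain, the same history. In the non-waivered H1b/H1c sample, use naloxone and referral history.
- **All four:** use only variables fixed before training, and exclude the Section H.d items collected in the post-training survey. Name the effect measure if a logit link is used. Report the unadjusted estimate as a sensitivity analysis.

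Pre-training Opioid Wizard use should not be added, since Section H.b.iv defines use only over the 6-month follow-up and an earlier measure is not planned.

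The cost is a few sentences of SAP text and a few degrees of freedom. One check is needed first: reconcile the Section H.c.i heading with Sections E.a and M, and confirm that the history is extracted for every randomized PCC. If it is, no new data source is required. The wording should be settled before outcome data are examined by arm.

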# E. Study Population

- a. Participants. Participants will be PCCs who practice at HealthPartners Clinics that have been previously randomized to the intervention arm of the parent study, Opioid Wizard. There will be 15 clinics randomized to receive the Opioid Wizard intervention. There are 225 eligible PCCs in the clinics randomized to the OUD-CDS. All randomized clinicians will be included in the analysis of Wizard use and prescribing and/or referral behavior (in event referrals are made to waivered clinicians).
- b. Inclusion and exclusion criteria. To be eligible for inclusion in this study, a PCC must practice at a study-eligible primary care clinic and be a family physician, general internist or adult-care non-obstetric nurse practitioner or physician assistant. PCCs are study-eligible regardless of whether they are waivered to prescribe buprenorphine.

**Sources or methods of recruitment.** For the parent study, PCCs will have the opportunity to participate in a webinar about general training of the Opioid Wizard tool. This webinar will include information about CDS alerts, printing the PCC and patient priorities, and using the tool within Epic's (EHR) active guidelines. At the end of the webinar, all eligible PCCs in intervention clinics will be notified about the opportunity to participate in additional case-based training on using Opioid Wizard, which they will receive an invitation to complete in their email. Up to three emails will be sent to PCCs from the MyLearning platform inviting them to participate in the training. The email will provide an introduction to the study and the elements of consent. We may also use additional strategies to encourage study participation, including asking clinic leaders to remind their PCCs to complete the training and directly emailing a final reminder before the initial survey closes. See **Appendix A** for recruitment email and **Appendix B** for the consent document. (Subsequent communications have been submitted separately as amendments.)

PCCs who complete the initial training via MyLearning (either the stigma reduction training or the comparison [attention control]) will be emailed a follow-up survey 3 months after they completed the initial training. PCCs will receive up to 4 emails to remind them to complete the follow-up survey. The recruitment email for the follow-up survey is available in **Appendix C**.

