#### H. Outcome assessment

**a.** Timing of outcome assessment. Immediately following training, PCCs will be asked to complete a brief (15-minute) follow-up survey via REDCap, a secure data

management software, to assess self-reported outcomes: stigma, waiver status, and, among non-waivered PCPs, intention to get waivered and intention to prescribe buprenorphine should a waiver no longer be required (see **Appendix D**). In addition, at 3 months following the training, PCCs will be asked to complete a follow-up survey via REDCap, to assess endurance of the stigma training on PCC stigma and intentions (see **Appendix E**). Opioid Wizard use will be pulled from CDS meta-data for each randomized clinician for encounters that are eligible for the Opioid Wizard intervention. PCC prescribing (number of MOUD, naloxone, and opioid prescriptions and the number of unique patients receiving prescriptions) and referral behavior will be extracted from the EHR. We will pull patient demographic information from the EHR to assess the extent to which provider behaviors differ across patient sub-groups, such as racial/ethnic groups, sex, and reason for intervention eligibility.

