# I. Post-recruitment retention strategies

- a. Participant retention. To encourage PCCs to complete the training, they will receive up to 4 reminders and will be offered a \$100 incentive. We may also ask clinic leaders to remind PCCs to complete training. Further, PCCs will be offered an additional \$25 incentive for completing the follow-up assessment at 3 months. Direct email communications will be sent to request and remind them about the survey. There may be volunteer bias in those who complete the training; however, this should not compromise internal validity as factors that predict participation should be random across intervention assignment. We will describe differences between completers and non-completers (e.g., gender, PCC type, waiver status, clinic).
- **b. Participant withdrawal.** Participants may withdraw from the study at any time. It is possible that they will not complete the training or the surveys. However, the training and surveys are designed to be short so they do not overburden participants.

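### The 3-month endurance analysis names no method for unreturned surveys and does not say that immediate post-training scores will be used

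*Combined protocol and SAP*

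**What the plan says.** Section H.a gives the 3-month survey its purpose: "to assess endurance of the stigma training on PCC stigma and intentions". Section M supplies the analysis: "we will examine whether the intervention has enduring effects on stigma and intentions by examining differences assessed at the 3-month follow-up survey". The modelling statement in the same paragraph is general: "A generalized linear model framework will be used to test the Aim 1 hypotheses". No repeated-measures term, use of the immediate score, imputation or sensitivity analysis is named for this outcome.

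Section E states that PCCs who complete the training "will be emailed a follow-up survey 3 months after they completed the initial training", and that "PCCs will receive up to 4 emails to remind them to complete the follow-up survey". Section I.b accepts non-return: "It is possible that they will not complete the training or the surveys". Section I.a notes possible volunteer bias among those who complete the training and argues that "this should not compromise internal validity as factors that predict participation should be random across intervention assignment". It adds: "We will describe differences between completers and non-completers (e.g., gender, PCC type, waiver status, clinic". Immediate stigma and intention scores are not among those examples.

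The difference, disdain and blame items and the two intention items appear in both surveys (Appendices D and E). Section K.a ties compensation to the immediate survey, and Section J.a gives each PCC a study identification number.

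**The concern.** A one-time-point comparison takes nothing from a PCC whose 3-month survey is missing. Yet nearly all of these PCCs will have answered the same items right after training. That answer is likely to be the best available predictor of the missing one, and it may also predict who replies.

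The argument in Section I.a concerns who completes the training. Return of the second survey comes after the arms have seen different content, so selection into it need not be alike in the two arms.

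The endurance claim is at stake. A reader will set the 3-month difference beside the immediate one, although the two may come from different sets of PCCs. If high-stigma PCCs fall away mainly from the stigma-reduction arm, a constant effect looks as if it grew. If low-stigma PCCs fall away from that arm, it looks as if it faded.

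**Working it through.** **Inputs.** From Section L: 146 PCCs (65% of 225), equal arms, two-sided 0.05. The documents give no return rate, between-survey correlation or selection strength. Assumed: 70% return (range 60% to 90%), correlation ρ = 0.7 (range 0.5 to 0.8), true difference 0.50 SD at both surveys.

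**1. The plan's own figure.** The nearest is Table 1, H1a. Detectable d ≈ (z₀.₉₇₅ + z_power) × 2/√N. For N = 146 at 80% power this is 2.802 × 2/12.083 = 0.464, or 0.467 with the t distribution; the table has 0.47. At 90% power the t value is 0.540; the table has 0.54. At 180 PCCs, 0.420 and 0.486 match 0.42 and 0.49. The cells for 112 PCCs (0.49 and 0.57) are not reproduced (0.534 and 0.618), but that is a separate matter and does not enter below. Table 1 gives no figure for the 3-month analysis.

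**2. Loss of responders.** With 146 PCCs, the detectable d at 80% power rises from 0.47 to 0.49, 0.52, 0.56 and 0.60 at 90%, 80%, 70% and 60% return.

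**3. Precision with no selection.** For return fraction r, the large-sample variance ratio (joint model to responder-only) is 1 − ρ²(1 − r). At r = 0.7:

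| ρ | Variance ratio | SE ratio | Responder-only SE larger by |
|---|---|---|---|
| 0.5 | 1 − 0.25 × 0.3 = 0.925 | 0.962 | 1/0.962 − 1 = 4% |
| 0.7 | 1 − 0.49 × 0.3 = 0.853 | 0.924 | 1/0.924 − 1 = 8% |
| 0.8 | 1 − 0.64 × 0.3 = 0.808 | 0.899 | 1/0.899 − 1 = 11% |

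Simulations with 146 PCCs put the joint standard error 3% to 4%, 8%, and 9% to 10% below the responder-only one, in agreement.

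**4. Bias with selection in one arm.** Suppose that in the stigma-reduction arm the log-odds of return fall by b per SD of immediate stigma. The mean immediate score among responders then shifts by −b × E[p(1 − p)]/E[p], where p is the return probability, and the 3-month mean shifts by ρ times that. With the intercept set for 70% return, numerical integration gives E[p(1 − p)] = 0.2033 for b = 0.4 and 0.1868 for b = 0.8.

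- b = 0.4: 0.7 × (0.4 × 0.2033/0.7) = 0.081, so the estimate is 0.58.
- b = 0.8: 0.7 × (0.8 × 0.1868/0.7) = 0.149, so the estimate is 0.65.
- b = 0.8 in the opposite direction: 0.50 − 0.149 = 0.35.

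If the intercept is instead held at logit(0.70) and selection acts on the raw score, return in that arm is higher (73% and 75%). The estimates are then about 0.57 and 0.62 to 0.63.

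**5. Similar selection in both arms.** With equal return rates the two shifts cancel and the estimate stays at 0.50. With a shared intercept and b = 0.8 the shifts are −0.179 and −0.228. The change is 0.7 × 0.049 = 0.034, giving 0.47.

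**6. Wider range.** A separate simulation used a true difference of −0.47, log-odds 0.7 per SD, return of 60% to 90%, and ρ of 0.5 or 0.7. Responder-only estimates ran from −0.29 to −0.65 under one-arm selection and from −0.46 to −0.48 under equal selection. Estimates using all immediate scores stayed at about −0.46 to −0.48 in every scenario.

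**The case against.** The plan nowhere limits the analysis to responders or rules out the immediate scores. A reader might infer that it does both, but that would be a reading of silence. What the text supports is that no method is named.

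A reader might also infer that any stigma-related dropout would pass for fading. Step 5 does not support this: a move from 0.50 to 0.47 is about 0.15 of a standard error (0.03/0.198, where 0.198 = 2/√102 for 102 responders). Material bias needs selection that differs by arm, and nothing in the documents shows that it will. Even then, a bias of 0.07 to 0.15 is 0.35 to 0.76 of a standard error.

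The success of the joint model in these scenarios is partly built in, because dropout was made to depend only on the immediate score. A between-arm difference at 3 months is also a legitimate measure of whether an effect is still present, so a test of change is an addition and not a correction. The reminders, the $25 incentive and the completion monitoring should hold dropout down.

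All of this stands as a limit on size. It does not supply a missing-data method. Retention measures reduce the problem without analysing it, and the precision gain in step 3 needs no selection at all.

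**Conclusion.** The gap is real and worth closing. For a stated question of the trial, the plan describes a single-time-point contrast and no treatment of unreturned surveys, although it collects the data that would improve on this. Under the assumptions above, the default contrast costs about 4% to 11% in standard error. Under one-arm selection of 0.4 to 0.8 log-odds per SD, it reads about 0.57 to 0.65 against a true 0.50.

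These sizes rest on assumed return, correlation and selection strength. They show what could happen and do not predict that it will. The finding should not be carried over to the primary H1a to H1c comparisons: those are made immediately after training and do not use the 3-month survey.

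**What to change.** In Section M, replace the 3-month-only comparison with a joint analysis of the immediate and 3-month responses on all PCCs with at least one survey.

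- **Stigma scales:** a repeated-measures model with arm, time, arm-by-time and an unstructured covariance.
- **Two intention items:** the same structure among non-waivered PCCs, with a model suited to a five-point response. State how a PCC who becomes waivered between surveys is treated, since Appendix E then skips the item on intention to get waivered.
- **Reporting:** the 3-month arm contrast as the endurance result, with the arm-by-time contrast as supportive. Tabulate return by arm and immediate score, so that readers can see whether selection differed.
- **Immediate score:** treat it as an outcome in the model and not as an adjustment covariate, because training has already affected it.
- **Sensitivity:** keep the responder-only difference.

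The cost is a few sentences and one standard model; no new data are needed. The downside is reliance on missing-at-random given the immediate score. Dropout driven by later attitudes beyond that score is not corrected.
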